3.3 Data collection

Stage 1b randomized pilot intervention trial (n=160):

Baseline data collection. After the informed consent process in a one-on-one interview (~60 minutes) using a computerized structured questionnaire, the interviewer will collect demographic information and detailed contact information (e.g., phone numbers, contact details of individuals who would know how to find the participant) to facilitate participant retention, and a venous blood sample for the alcohol biomarker measure (PEth).

Interviewers will set the appointments for the 3- and 6-month follow-up.

3 and 6-month follow-up data collection. For participants' convenience the 3-month follow-up interview may be conducted by phone whereas the 6-month follow-up interview must be in person since it involves obtaining a venous blood sample. For the 6-month follow-up, study interviewers will conduct follow-up data collection either at the study office at the clinic or, if requested by the participant, by meeting at a location of the participant's choosing. In our prior work in Uganda, we have found that participants who may have challenges in coming to the study office prefer to have the interviewer come to them. At 3- and 6-month follow-up the interviewers will conduct an individual structured interviewer-administered computer-based interview (~45 minutes duration). At the 6-month follow-up they will also collect 2mls of venous blood for PEth testing. If participants cannot be reached for the blood sample, we will still conduct the interview over the phone. This will allow us to still obtain some 6-month follow-up data from all participants. However, we will continue to follow up with these participants to obtain the venous blood sample even after the phone interview. Follow-up interviewers will be blinded to study arm assignment.

Dried blood spot (DBS) collection and testing. During the baseline and 6-month follow-up interviews, 2mls of venous blood will be collected using sterile EDTA tubes and transported to a laboratory within 6-10 hours from the time of sample collection. At the laboratory, 50µl drops of blood will be placed onto Whatman 903 filter paper (DBS cards), allowed to dry for ≥3 hours, and then stored packaged with a desiccant in a -80C freezer at Mildmay laboratory.⁴⁴ Since no laboratories in Africa conduct PEth testing, PEth testing will be done at the United States Drug Testing Laboratories using liquid chromatography-tandem mass spectrometry (LC/MS/MS).⁴⁵ We will obtain a Materials Transfer Agreement to ship the DBS to the U.S.

Monitoring intervention fidelity. We will audio record all intervention sessions and randomly select 20% of them to code for fidelity to the intervention protocol.

Training of research assistants and interviewers

To collect baseline and follow-up interview data for the intervention, experienced research assistants/interviewers will be hired for the purposes of the study. These individuals will be trained in the study procedures by one or more of the investigators. Interviewers will be individuals qualified and experienced in performing phlebotomy because they will be responsible for the blood draws and venous blood collection for PEth testing. Clinic staff will also be oriented to the study and the study procedures by the investigators.

Training of counselors in the intervention protocol

Counselors will be trained to deliver either screening and referral (enhanced control) or the *KISOBOKA* intervention. Counselors will have an advanced high school (college preparatory) or college education and have training in general counseling skills. The counselors who will deliver the intervention will undergo a 4-day criterion-based training. In our prior MI-based intervention in Uganda we successfully trained laboratory technicians in MI principles⁴⁶ thus we are confident that counselors will be able to learn and become proficient in MI counseling skills through our training. Using highly trained clinical psychologists is not generalizable nor sustainable in this setting since very few of such professionals exist in Uganda.

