3.2 Study design and procedures

Intervention

Recruitment, eligibility screening, and informed consent.

We will recruit men who are patients at Mildmay's HIV clinics in Wakiso District using two methods.

- 1) After a male patient checks in for his appointment and his HIV clinic record is pulled, a clinic staff member will review the patient's records to determine if they may be potentially eligible (male, aged 18-50, on ART for at least 6 months, work in the fishing industry, can be reached by phone). After the patient has completed his clinic appointment, clinic staff will refer male patients who are potentially eligible to a research assistant for eligibility screening.
- 2) Clinic staff will also review clinic records to identify potentially eligible patients and will call the patient to tell him about the study. If the patient is interested, they will seek permission to share his phone number and name with the researchers, provide the contact number for the research assistant, and offer that the patient can come to the clinic to meet the research

assistant to learn more about the study. Study staff will briefly describe the study and seek informed consent to conduct eligibility screening.

Those determined eligible will be offered participation in the study and study staff will obtain written informed consent.

Intervention content and structure

After participants complete the baseline structured interview, the research assistant will refer them to the appropriate counselor who will provide intervention participants with the *KISOBOKA* ("It is possible!"). Our proposed brief intervention consists of 4 sessions: 2 individual, 2 group over 6 weeks, plus 2 times weekly text message reminders of life/savings (family prosperity, opportunities for children) and healthy living goals. Through these sessions the combination intervention will address environmental, interpersonal, and individual level factors which are key drivers of alcohol use and key barriers to HIV care engagement and adherence in this population.

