Session 1, at enrollment, In-person individual session combining MI-based counseling and goal setting and setting up the structural component of the intervention. During session 1 the counselor will: (1) Set-up the participant to receive payments for work via mobile and (if necessary) helping the participant set up a free mobile money account; (2) discuss short and long term life and healthy living goals, financial planning and savings goal setting (e.g., % of income to reach target savings amount in X time), set goal to transfer X% of daily earnings to a savings account, establish a separate healthcare savings; (3) feedback about AUDIT-C score and assess barriers to HIV care engagement and adherence; (4) MI-based counseling about alcohol use and HIV care engagement and adherence to develop discrepancy between their behavior and savings/life and health goals, engage client in change talk including setting specific goals, discussing barriers, and ways to overcome barriers; (5) discuss alcohol-free leisure activities; (6) provide a diary for participant to track spending and savings and time and money spent drinking.

Session 2, 2 weeks after enrollment, MI-based individual session via phone. Counselors will call participants and will: (1) review progress on alcohol and HIV care engagement and adherence goals, additional counseling as needed to set new goals, overcome barriers or reinforce positive behaviors; (2) review spending and saving diary and progress on savings; (3) review participant's receipt of work payments via mobile money, progress on savings goals, and help troubleshoot any problems.

Sessions 3 and 4, approximately 4 and 6 weeks after enrollment, Group sessions with 4-8 participants per group. Each session will consist of a counselor-led group discussion: (1) encouraging participants to share with the group their life and savings goals, experience with savings, motivations to save, benefits to saving, and long term planning for healthy living; (2) discussing alcohol-free leisure activities and generate motivation to engage in alcohol-free leisure activities; (3) reinforce discrepancy between risky alcohol use and not being engaged in care, not adhering to ART, and long term goals; (4) group "problem solving" about overcoming challenges to reducing alcohol use, including participating in alcohol-free leisure activities, HIV care engagement, and ARV adherence including HIV stigma.

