Text message reminders. Intervention arm participants will receive 2 times weekly text message reminders of their goals to increase the salience of delayed rewards of saving money and healthy living. Timing will be approximately 1 hour prior to when the participant reports usually drinking. For confidentiality reasons the text message reminders will not address alcohol, HIV care engagement, or adherence specifically but more broadly focus on "healthy living". We chose the frequency of 2 times weekly based on data showing this frequency is the most acceptable and effective in adherence studies.^{20, 21}

Intervention participation incentives. Based on San Diego State University IRB guidance we will compensate participants specifically for the time involved in participation since participation may require them to take time away from work. The intervention arm involves significantly more time commitment (approximately 563 minutes) than the control arm (approximately 195 minutes) and participants will be compensated accordingly. The per hour rate (18,000 Shillings, ~ \$5) will be equivalent between study arms. We detail participant incentives below:

Control group: Alcohol screening and referral. Control condition participants will complete the baseline questionnaire, which includes the AUDIT-C screening for risky alcohol use. After completing their baseline assessment, enhanced control condition participants will receive very brief feedback on their AUDIT-C score according to the feedback suggested in the AUDIT brief intervention manual,²² be provided a referral for alcohol counseling, and briefly engaged in discussion of the importance of HIV care engagement and adherence according to the MOH protocol.²³ The control session will last approximately 20 minutes. The control is an enhanced treatment as usual arm which is recommended for feasibility and preliminary efficacy studies.²⁴

Sample size for randomized pilot intervention trial

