We will conduct a stage 1b pilot randomized controlled trial of the intervention. As a pilot study, this study is not powered to detect differences in outcomes, but rather to obtain reliable estimates of effect sizes for a subsequent efficacy trial. However, for illustrative purposes we explore power assuming a small effect size ($d= 0.2$) which is consistent with most brief MI-based alcohol intervention study effect sizes^{17, 25-27} as well as care engagement interventions.²⁸⁻³² **We plan to enroll 160 participants in the pilot intervention trial** with 80 in each arm i.e., randomizing to the KISOBOKA intervention arm (n=80) or to the control arm (n=80, alcohol screening and referral). To be conservative we anticipate 25% attrition. This will provide 72% power to detect an intervention effect and 85% power to detect a study arm x time effect.

Sampling procedure for the randomized pilot intervention trial (n=160).

The participants recruited (based on the inclusion and exclusion criteria) from the Mildmay HIV clinics in Wakiso District will be requested to share the research assistant's contact details (phone numbers) with their potentially eligible friends. This snowball-sampling procedure will enable us to reach more participants in this hard-to-reach population. Those interested in participating in the study will contact the research assistant who will then take them through subsequent eligibility screening and recruitment procedures. This process will be repeated until the required sample is attained.

Randomization for stage 1b randomized pilot intervention trial.

Individual-level randomization with permuted block assignment balancing 1:1 will be used to create equal size groups for the two study arms. Blocks of 8 or 10 study-generated ID numbers will be created and randomly assigned to intervention or control. Once a participant is screened as eligible and attends an enrollment/baseline visit they will be assigned a study-generated ID number from the pre-randomized list which determined their study arm assignment.

Study variables

Dependent variables

Primary outcomes:

- Phosphatidylethanol (PEth) (alcohol biomarker, blood sample)
- AUDIT-C score¹⁹
- ART adherence³³

Secondary outcomes:

- HIV care engagement
- HIV viral load obtained from clinic records
- Frequency of heavy/binge drinking

Potential covariates

- Receipt of instrumental and emotional social support³⁴

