Data security: Data directly entered from the questionnaire interviews will be automatically encrypted and then uploaded onto a secure server. Only the PIs and data manager will have access to the server. No participant names will be stored in the database. All participants will be identified by a unique identifier, a random number assigned to them at the time of recruitment. In the event of loss of data or theft, all data files will be encrypted, and no outside user would be able to access the data. To ensure that no data that is collected is lost, encrypted data will be backed up on several sources: a separate server and copied to a secondary encrypted database used by the PI and biostatistician for additional processing.

Statistical Analysis Plan

A key objective of this study is to explore the effectiveness of the intervention vs. control and obtain effect size estimates to be used to design a future trial of this intervention. The primary outcomes are PEth scores, AUDIT-C score, and ARV adherence. Different statistical methods will be utilized depending on the type of outcome variable and whether minimum conditions for use of the methods are met. For example, log Gamma models may be used to analyze the difference in PEth scores between intervention and control groups given the expected distribution of PEth scores. An intent to treat approach will be utilized to determine analytic sample. Variables (except PEth which is measured at 2) will be measured at three time points (baseline, 3 and 6 months) so the dependency from the repeated measures must be considered. Information criterion such as AIC and BIC will be used to select the most appropriate covariance structure to address dependence. Generalized estimating equations (GEE) will be built to examine the intervention effect on our outcomes of interest across time points (baseline, 3 and 6 months), adjusting for repeated measurement, using a time*condition interaction term. Potential covariates for each adjusted model will be identified a priori from the literature and added to the model. Correlation matrices will be determined based on model fit. Statistically significant covariates will be retained in final fitted models using an alpha of 0.05.

4 Ethical considerations

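### Counselors appear to serve one arm only, but the planned GEE allows only for repeated measures on a man, so intervals meant to inform a later trial may be too narrow

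*Combined protocol and SAP*

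**What the plan says.** All references are to the combined protocol and SAP.

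- **Allocation** (3.2, Randomization): "Individual-level randomization with permuted block assignment balancing 1:1 will be used to create equal size groups for the two study arms".
- **Route to a counselor** (3.2, Intervention content and structure): after the baseline interview, "the research assistant will refer them to the appropriate counselor who will provide intervention participants with the" KISOBOKA sessions.
- **Who delivers what** (3.3, Training of counselors): "Counselors will be trained to deliver either screening and referral (enhanced control) or the" KISOBOKA intervention. A longer training is described for one set only: "The counselors who will deliver the intervention will undergo a 4-day criterion-based training".
- **Contact in each arm** (3.2): the intervention has an individual session, a phone session and two counselor-led sessions described as "Group sessions with 4-8 participants per group", plus text messages. The control arm has one contact: "The control session will last approximately 20 minutes".
- **Analysis** (3.5, Statistical Analysis Plan): the dependence named is within the man, "so the dependency from the repeated measures must be considered". The GEE estimates the intervention effect "adjusting for repeated measurement, using a time*condition interaction term".

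No counselor term, counselor-level clustering or related sensitivity analysis is planned, and counselor is not among the potential covariates in 3.2. The number of counselors and any counselor ICC are not stated. The purpose given in 3.2 and 3.5 is to obtain effect sizes for designing a later trial.

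**The concern.** Randomising men individually does not make their outcomes independent once treatment starts. Men who see the same counselor share that counselor's skill and style. If this affects outcomes, their results are correlated, and a GEE clustered on the man treats them as independent. The between-counselor part of the variance is then missing from the standard error of the arm contrast.

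There is a second consequence. If no counselor works in both arms, a difference in average skill between the two sets falls wholly into the arm contrast. No model can separate the two.

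What is at stake is the precision that the pilot may claim. A later trial may use other counselors. An interval that holds only for the present ones would overstate how well the effect is known for that purpose. Allowing only for the session groups would not cover this: those groups exist in one arm and in two of the four sessions.

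**Working it through.** The plan gives no figure for counselor clustering, so there is none to reproduce. The power figures in 3.2 are not used here.

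**Inputs from the documents.** 80 men per arm and 25% anticipated attrition (3.2, Sample size): 80 × 0.75 = 60 analysed per arm.

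**Assumptions, because the documents are silent.** K counselors per arm with K = 2, 3 or 5; equal caseloads m = 60/K; counselor ICC of 0.01, 0.02 or 0.05; each man assigned to one counselor; nominal two-sided 5% test.

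**Formulas.**

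- Design effect in a clustered arm: DEFF = 1 + (60/K − 1) × ICC.
- Variance ratio V of the arm contrast: (DEFF + 1)/2 if only the intervention arm is clustered, DEFF if both arms are.
- Interval width ratio: √V.
- True error rate: 2 × P(Z > 1.96/√V).

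**Worked case, K = 3, ICC 0.05.** DEFF = 1 + 19 × 0.05 = 1.95.

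- Intervention arm only: V = (1.95 + 1)/2 = 1.475, √V = 1.21, error 10.7%.
- Both arms: V = 1.95, √V = 1.40, error 16.0%.

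**Intervention arm only: error rate (width ratio).**

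| ICC | K = 2 | K = 3 | K = 5 |
|---|---|---|---|
| 0.01 | 6.7% (1.07) | 6.1% (1.05) | 5.6% (1.03) |
| 0.02 | 8.4% (1.14) | 7.2% (1.09) | 6.3% (1.05) |
| 0.05 | 13.6% (1.31) | 10.7% (1.21) | 8.3% (1.13) |

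**Both arms equally clustered (upper bound): error rate (width ratio).**

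| ICC | K = 2 | K = 3 | K = 5 |
|---|---|---|---|
| 0.01 | 8.4% (1.14) | 7.2% (1.09) | 6.3% (1.05) |
| 0.02 | 11.9% (1.26) | 9.5% (1.17) | 7.6% (1.10) |
| 0.05 | 21% (1.57) | 16.0% (1.40) | 11.5% (1.24) |

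**On the effect-size scale.** For a plain comparison of two means, the unclustered half-width is 1.96 × √(2/60) = 0.36 SD. At ICC 0.05 with clustering in the intervention arm only, it becomes 0.47, 0.43 and 0.40 SD for K = 2, 3 and 5. The GEE's own width will differ, because it depends on the within-man correlation.

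**Where the effect fades.** At ICC 0 nothing changes. With 10 counselors per arm at ICC 0.05, DEFF = 1 + 5 × 0.05 = 1.25; the error is 6.5% (intervention arm only) or 8.0% (both arms).

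**Comparison with session groups.** At ICC 0.05, groups of 4 to 8 give DEFF from 1 + 3 × 0.05 = 1.15 to 1 + 7 × 0.05 = 1.35. Counselor caseloads of 30, 20 and 12 (K = 2, 3 and 5) are larger clusters; a caseload of 6 (K = 10) is not.

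**The case against.** The case on the other side is substantial, and much of it stands.

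- **Tempting reading: the intervals are too narrow, without qualification.** The documents do not support this. It requires an ICC above 0 and inference beyond the present counselors. For these counselors taken as fixed, the unadjusted interval can stand.
- **Tempting reading: an error of 16% to 21% is the expected size.** Those figures need ICC 0.05 in both arms and only 2 or 3 counselors per arm. The control contact is a single short session with manual-based feedback, a referral and a brief discussion following the health ministry's protocol. An ICC equal to that of a four-session counseling intervention is unlikely there.
- **Tempting reading: counselor skill must vary widely because the staff are untrained.** Section 3.3 requires training in general counseling skills, and the intervention training is criterion-based. All intervention sessions are recorded and 20% are coded for fidelity. These steps may reduce variation between counselors. They do not correct a standard error, and the fidelity coding is not described for control sessions.
- **Tempting reading: each man has one counselor throughout.** Section 3.2 does not say that the same counselor delivers all four sessions. If they differ, a caseload of 60/K only approximates the cluster structure.
- **Tempting reading: the design is wrong.** One-arm counselors are a defensible guard against contamination. The gap is in analysis and reporting.

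The study is also a pilot that is expressly not powered to detect differences, so test error is not its main measure. That limits the weight of the point but does not remove it: the same variance ratio governs the interval around the effect size, which is the pilot's stated product.

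**Conclusion.** The point holds conditionally. Counselors appear to be trained for one arm only, and the planned GEE has no counselor level. If the counselor ICC is above 0 and the result is to carry over to other counselors, the intervals may be too narrow, and counselor skill and arm cannot be separated.

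The most reasonable range takes clustering to lie mainly in the intervention arm. The interval should then be about 1.13 to 1.31 times as wide at ICC 0.05, and 1.03 to 1.07 times at ICC 0.01, for 5 to 2 counselors per arm. The low end is negligible and the high end is not. The documents cannot decide between them, because both the number of counselors and the ICC are assumed. This is a worthwhile improvement to what the pilot reports; it does not invalidate the design or the planned main estimate.

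**What to change.** 1. **Section 3.3.** Record the ID of the counselor delivering each session, in both arms, and the session group. Report the number of counselors per arm and their caseloads.
2. **Section 3.5.** Keep the planned GEE as the main analysis. For each primary arm contrast, add a pre-specified sensitivity interval that allows for counselor clustering, using actual caseloads and ICC 0.01, 0.02 and 0.05. Show clustering in the intervention arm only first, and in both arms as the upper bound. Fixed ICC values are suggested because there may be too few counselors for reliable cluster-robust errors. If sessions for one man are delivered by different counselors, state in advance which counselor defines the caseload.
3. **Reporting.** State that the unadjusted interval applies only to these counselors, and that counselor skill and arm cannot be separated. Consider the wider interval when sizing the next trial.

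The cost is two kinds of ID field and a few lines of SAP text, with no change to recruitment or to how counselors are assigned. The downside is a wider interval that rests on an assumed ICC. The sensitivity interval addresses precision only; the confounding of skill with arm can be disclosed but not removed.
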